For evaluation purposes and measures of walking progression, reliable and valid measures will be utilized to assess: a) lower extremity voluntary control; b); degree of walking independence; and, c) walking speed, endurance and temporal-spatial parameters.

- Assessment of strength, spastic motor behaviors and functional ambulation will be performed by a licensed physical therapist at the initial evaluation and during walking protocols.
 Assessment includes:
- Lower Extremity Motor Scores: to determine strength in the lower extremities

- Functional Independence Measure (FIM): extent of disability and societal limitations linked with functional limitations of ambulation.
- 10m walk: gait speed
- 6min walk: gait speed and distance
- GaitMat II (Equitest, Chalfont, PA): to detect temporal-spatial gait patterns.

B. Objective measure of motor and walking performance

Evaluation of the changes in walking performance with the use of the proposed WAD will be assessed using computerized gait analysis during independent stepping on an instrumented treadmill and during over ground walking. Specific outcome measures include: a) extent of lower extremity loading and ground reaction forces during independent treadmill stepping; c) peak treadmill speed at minimal body weight support; c) lower extremity kinematics during stepping, including peak hip, knee, and ankle joint kinematics during walking, and temporal-spatial gait parameters, and, d) timing of lower extremity EMG activity during treadmill stepping. In addition, metabolic costs will be determined. Metabolic costs will be collected using a portable metabolic system (K4b2, CosMed USA, Inc., Chicago). Metabolic measures will be obtained in sitting for 5 minutes prior to walking. Metabolic measures will be taken during un-assisted walking and device assisted walking for comparison. Subjects will return to their metabolic baseline between the walking trials. Metabolic measures will always be measured at sub-maximal levels and will be stopped 75% of target heart rates. Written approval from subject's physician will be obtained before allowing subjects to participate in sub-maximal graded treadmill test. Non-approval from physician will exclude the subject's participation only in the sub-maximal graded treadmill test; however they will be allowed to participate in the other tests involved in the study. Gait analysis

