Transcranial magnetic stimulation (TMS) will be performed while walking with and without the WAD. TMS is a safe, non-invasive, painless method of brain stimulation that has been widely used to study the physiology of the representations of muscles in the motor cortex in healthy and neurologically disordered individuals. Very short duration (< 1 ms) magnetic pulses are applied via an insulated wire coil placed on the intact scalp overlaying the motor cortical. Each pulse induces a motor evoked potential (MEP) in a target muscle that can be readily monitored by recording EMG from the muscle. Magnetic stimuli will be delivered from a Magstim 200 unit via a Magstim double cone coil (Magstim Company, Boston MA). Self adhesive disposable electrodes (Suretrace) with an inter-electrode distance of 2 cm will be applied over the muscle bellies of the quadriceps, hamstrings, ankle dorsiflexors and ankle plantar flexors in the lower extremities. A ground electrode will be applied over the patella. Standard skin preparation techniques (light abrasion and cleansing with alcohol) will be completed prior to application of the electrodes. EMG recordings will be amplified (Octopus AMT-8; Bortec Biomedical, Calgary, Alberta), band-pass filtered (10-1000 Hz), and sampled at 5000 Hz. Electromyographic (EMG) activity will be collected from all muscles bilaterally. TMS will be delivered with the stimulating coil positioned over the vertex at intensities ranging from 70 - 140% of "walking threshold". This threshold is a better estimate of excitability than conventional thresholding because during walking, EMG burst patterns and EMG amplitude differ between subjects, and walking threshold is typically lower than tonic contraction threshold, and much lower than rest threshold. Walking threshold is the stimulus intensity that results in MEPs just visible as time locked waveforms emerging out of background EMG. Pre-burst onset MEPs will also be recorded at an intensity that results in a MEP of ~ 500 μ V. This measure is important because we expect when the WAD is providing assistance, the

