EMG burst amplitude may change, making it difficult to interpret changes in MEP amplitude assessed during the EMG burst. Subjects will be walking on a treadmill when magnetic stimulation is delivered. An optical motion switch will detect when a limb is in mid-swing and sends a pulse to software that in turn delays a TMS trigger pulse to coincide with a chosen cycle phase. Motor cortex excitability changes during walking will be examined by calculating the mean amplitude of 10 MEPs recorded from each muscle with and without WAD. A harness will be placed around the subject's pelvis and lower torso. The harness is attached to a rope and pulley system that is capable of supporting the subject's entire body weight in the upright position. A physical therapist (PT) will be in attendance at all times. Use of the harness and handrails, and the PT in attendance, will ensure that the subject is comfortable and secure at all times. Subjects will be provided with sufficient breaks between walking to avoid fatigue.

IV. Using the Walk Assist Device (WAD)

As part of the testing in this study, subjects will be asked to participate in body weight supported treadmill walking and/or over ground walking with the help of the WAD. All testing procedures will be with a licensed physical therapist or physical therapist assistant as described below.

Device Assisted Walking: The walk assist device (WAD) consists of a waist frame, rechargeable lithium ion batteries, hip actuators / motors, angle sensor and thigh frame. The WAD gently assists both forward and backward movements at a person's hip joints in a very smooth way with the electrical actuators. The electrical actuators are equipped with angular sensors to monitor walking speed, velocity, and the degrees of the forward and backward movement of the hip joints. Using the information from the sensors, the WAD gently assists the person towards normal walking patterns. However, most subjects are unaware of this manipulation because the assistive torque is

Study Number # NUSTU00022438

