small. The WAD stops functioning when the subject stops walking and will in no way control walking or movement of the subject causing tripping or falling. The total weight of the WAS is approximately six pounds. All subjects will receive a thorough explanation of the structure and function of the WAD before the experiment to eliminate any concerns. Individual fitting of the WAD will be performed by the persons who developed the WAD to avoid any kind of discomfort to the subjects. The WAD also helps in conserving the subject's energy consumption during walking as the device utilizes the subject's inertia and gravity to assist walking. The WAD has been successfully used to assist walking in the elderly population and reduce energy consumption during walking in healthy controls.^{1, 2}

IV. Statistical Analysis

Paired comparisons of electromyographic, kinematic, kinetics, strength and metabolic data will be made within subjects between groups (un-assisted stepping, device-assisted stepping) using standard parametric (t-test, ANOVA) comparisons. Changes in clinical performance will be assessed using primarily ordinal measures, with statistical comparisons made using non-parametric tests. Correlation (Pearson or Spearman) will be made between clinical/functional assessments and kinematics/kinetics observed during device-assisted walking.

V. References

1. Effects of an automated stride assistance system on walking parameters and muscular glucose metabolism in elderly adults. Shimada H, Suzuki T, Kimura Y, Hirata T, Sugiura M, Endo Y, Yasuhara K, Shimada K, Kikuchi K, Oda K, Ishii K, Ishiwata K. Br J Sports Med. 2008 Nov;42(11):622-9. Epub 2008 Feb 28.

2. The use of positron emission tomography and [18F]fluorodeoxyglucose for functional imaging of muscular activity during exercise with a stride assistance system.Shimada H, Kimura Y, Suzuki T, Hirata T, Sugiura M, Endo Y, Yasuhara K, Shimada K, Kikuchi K, Hashimoto M, Ishikawa M, Oda K, Ishii K, Ishiwata K. IEEE Trans Neural Syst Rehabil Eng. 2007 Sep;15(3):442-8.

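### The order of un-assisted and device-assisted walking is not set, randomised or recorded, and no period term is named, so the plan permits an order effect to be read as a device effect

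*Combined protocol and SAP*

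**What the plan says.** The device is evaluated by comparing each subject with himself or herself. The section headed IV. Statistical Analysis (the second section numbered IV) states: "Paired comparisons of electromyographic, kinematic, kinetics, strength and metabolic data will be made within subjects between groups (un-assisted stepping, device-assisted stepping"), using t-test or ANOVA. It lists no factors for the ANOVA.

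The measurement sections name both conditions but no sequence:

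- Section III.B, metabolic cost: "Metabolic measures will be taken during un-assisted walking and device assisted walking for comparison".
- Section III.C, corticospinal excitability: "Transcranial magnetic stimulation (TMS) will be performed while walking with and without the WAD". The outcome is obtained by "calculating the mean amplitude of 10 MEPs recorded from each muscle with and without WAD".

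Two safeguards bear on the point. For the metabolic measures, "Subjects will return to their metabolic baseline between the walking trials". In the section on magnetic stimulation, "Subjects will be provided with sufficient breaks between walking to avoid fatigue". Neither gives a duration, and neither says which condition comes first.

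Section II gives 12 subjects as sufficient and 15 to be recruited. It divides subjects into two gait-speed strata at 0.4 m/s.

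**The concern.** In a two-condition within-subject comparison, the paired difference contains the device effect and whatever changes between the first and second walk. Subjects with chronic stroke who walk at 0.8 m/s or slower are asked to step in a harness on an instrumented treadmill at several speeds. Practice, habituation to the treadmill or residual fatigue could plausibly shift the second set of recordings.

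If everyone walks in the same order, that shift is added to the device effect in every subject. A period term cannot then be estimated, because period and condition are the same variable. The error could run either way: an order effect reported as a device effect, or a real device effect hidden. If the order varies by convenience and is recorded, an additive effect can be adjusted for afterwards with some loss of power. If it varies and is not recorded, it cannot.

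**Working it through.** **1. What the document contains.** Sections III.B and III.C and the Statistical Analysis section were set side by side. All compare the two conditions within subjects. None states an order, a method of balancing it, or a record of it. None names a period or sequence factor. These sections are present in full, so the silence is not due to removed text.

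**2. The plan's own figure.** 12/(1 − 0.20) = 15, so 12 and 15 agree if 20% attrition is implied. The 12 itself cannot be reproduced, because no alpha, power, effect size or SD is given. Assuming two-sided 0.05 and 80% power, a paired t-test with n = 12 (11 df) detects d = 0.889 SD of the paired difference. That value is used below.

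**3. Model.** D = δ + e·s + ε, where D is device minus un-assisted, δ is the device effect and e the order effect. s is +1 if the device comes second and −1 if it comes first, and ε has SD 1. All effects are in SDs of the paired difference. The documents give no value for e, so 0.3 and 0.5 are assumptions.

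**4. One fixed order, plain paired t-test** (device second for all; noncentral t, 11 df, critical value 2.201, noncentrality (δ + e)√12):

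| True δ | e | Noncentrality | Rejection rate |
|---|---|---|---|
| 0 | 0.3 | 1.039 | 15.8% |
| 0 | 0.5 | 1.732 | 35.3% |
| 0.889 | −0.3 | 2.039 | 46.1% |
| 0.889 | −0.5 | 1.346 | 23.4% |

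The first two rows are false positives. The last two are power when the order effect opposes a true device effect, against 80.0% with no order effect.

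**5. Varied order with a period term.** The estimate is the mean of the two order-group means, which cancels e. SE = √[0.25(1/n₁ + 1/n₂)], with 10 df and critical value 2.228. Power at d = 0.889:

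| Split | SE | Noncentrality | Power |
|---|---|---|---|
| 6/6 | 0.289 | 3.078 | 79.2% |
| 7/5 | 0.293 | 3.035 | 78.1% |
| 8/4 | 0.306 | 2.902 | 74.4% |
| 9/3 | 0.333 | 2.666 | 67.2% |

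In simulation (200,000 runs per cell), the period-adjusted test holds its level at 4.9% to 5.0% for 6/6 and 5.0% for 9/3. A plain paired t-test on a 9/3 convenience split gives 6.7% (e = 0.3) or 9.2% (e = 0.5).

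**6. Likely splits after attrition.** Blocks of two within two strata start 15 recruits at 8/7. With 3 random losses there are C(15,3) = 455 outcomes:

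- 6/6: 28 × 7 = 196, or 43.1%.
- 7/5 either way: 8 × 21 + 56 = 224, or 49.2%.
- 8/4: 35, or 7.7%.

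Average power is (196 × 79.2 + 224 × 78.1 + 35 × 74.4)/455 = 78.3%.

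**7. What balancing does not cure.** If carry-over of size L affects one order only, the estimate is biased by L/2. At 6/6 the noncentrality is (L/2)/0.289, which gives 7.6% false positives at L = 0.3 and 12.3% at L = 0.5.

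**The case against.** The strongest reply is that silence is not a fixed order. The plan does not rule out balancing, and an ANOVA with unlisted factors could include period. A reader might infer that all subjects will be tested in one sequence, or that a period analysis is excluded. The text supports neither: both are unspecified. This stands, and it makes the false-positive figures conditional. It does not answer the point, because a period term works only if the order varies between subjects, and that must be settled before testing.

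The safeguards also count. Return to metabolic baseline should deal with much of any metabolic order effect, and breaks limit fatigue during magnetic stimulation. Practice, habituation and after-effects of the device remain. In addition, section III.B calls for at least three 30-second recordings at various speeds. Interleaving the conditions could change the size of an order effect and how period is coded, but the plan does not say whether trials are blocked or interleaved.

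A further inference is that recordings from different surfaces or speeds would be paired, since gait is assessed "during independent stepping on an instrumented treadmill and during over ground walking". The documents do not support this. Pairing like with like is the ordinary reading of a paired comparison with preset 0.5 km/hr steps, and for magnetic stimulation the surface is fixed: "Subjects will be walking on a treadmill when magnetic stimulation is delivered". Nor is the metabolic section without any surface: it mentions a sub-maximal graded treadmill test, although it does not say that the comparison walks are that test. This calls for clarification only.

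**Conclusion.** The point holds as a design gap that should be fixed before data collection. The order of conditions is neither set, balanced nor recorded in the plan, no period term is named, and the text permits a sequence that would confound order with device beyond repair. That conclusion follows from the design and needs no number.

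The 16% and 35% show sensitivity and are not estimates for this trial. They require n = 12, two-sided 0.05, the same order for all subjects, and an additive order effect of 0.3 or 0.5 SD. None of these except the sample size is in the documents. It would be wrong to conclude that the device comparisons are biased; the plan leaves them unprotected.

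**What to change.** Before data collection:

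- Randomise each subject to un-assisted-first or device-first, balanced overall and as far as possible within the two gait-speed strata of section II, for example in blocks of two per stratum.
- Apply the allocation to every test battery that compares the conditions: gait and EMG, metabolic, and magnetic stimulation.
- Record the order actually used.
- Analyse the parametric outcomes with subject, condition and period terms. The ordinal clinical measures, which go to non-parametric tests, are not covered by this model.
- State differential carry-over as a limitation.

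As a minor clarification, state that recordings are paired on the same surface and speed step, and say whether the metabolic comparison walks are the sub-maximal graded treadmill test.

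The cost is an allocation list, a few protocol sentences and, under the assumptions above, a fall in power from 80.0% to about 78.3% on average over the likely splits. No extra subjects are needed. The effect on visits cannot be checked, because the document gives no visit schedule.
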